- have a cochlear implant
- have chronic tinnitus
- have temporomandibular joint disease
- have been diagnosed with traumatic brain injury
- have been diagnosed with neurological disease other than headaches

- have a diagnosed vestibular dysfunction and/or balance dysfunction
- have a history of abusing alcohol or other drugs
- are experiencing medication overuse headaches (individuals with respect to whom the principal investigator is concerned that analgesic abuse is involved based on the ICHD-II guidelines).
- are less than 18 years old or greater than 65 years old
- have had eye surgery within the previous three months or ear surgery within the previous six months
- have active ear infections or a perforated tympanic membrane
- have participated in another clinical trial within the last 30 days or are currently enrolled in another clinical trial
- are using Botulinum toxin-based treatments for migraines or for facial cosmetic reasons.
- are taking anti-emetics chronically (more than 2 times per week, consistently)
- Though not excluded, subjects taking anti-histamines will be encouraged not to take such medications within four hours prior to a CVS treatment. The investigator should review other medications taken by the subject with properties that mimic anti-nausea or anti-dizziness drugs as these may reduce responsiveness of the vestibular system to caloric stimulation. Such medications should also be avoided within four hours prior to a CVS treatment.

- **Withdrawal Criteria**

- Subjects must be withdrawn from the clinical trial if any of the following events occur:
 - Surgery during the study period.
 - A subject does not continue to meet inclusion/exclusion criteria.
 - A subject is significantly non-compliant with the requirements of the protocol (principal investigator & sponsor decision).
 - The subject does not complete at least 25 of 28 daily diary entries in her/his headache diary during the baseline period. (That is, the subject must be compliant with maintaining the headache diary.)
 - A subject becomes pregnant during the trial as evidenced by a positive pregnancy test.
 - The subject develops an illness (adverse event) that would interfere with his/her continued participation.
 - The subject withdraws his/her consent.
 - The principal investigator feels that it is the subject's best interest to be withdrawn.
 - Scion Neurostim discontinues the study or has achieved the targeted enrollment.

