- (i) **Screening & Baseline Period:** Once the subject has been established as having the appropriate pre-treatment history, she/he will be asked to complete a review of the informed consent. If the subject agrees to participate in the study, the subject will then complete a screening visit. The study coordinator will complete a headache history questionnaire for the subject. If the subject is recommended for continuation in the study after the screening visit and tentatively approved by a principal investigator, she/he will start a daily headache diary and continue to make entries for twenty-eight consecutive days. Subjects will be given Scion email accounts to be used for submitting headache diary entries. Sites will assist subjects with syncing their Scion email accounts with their smartphones or tablets, and will ensure that subjects can competently take a photo of the ediary form, upload and send according to procedure. If the subject does not complete at least 25 of 28 daily headache diary entries during the baseline period, she or he will be withdrawn and will not proceed to randomization.
- (ii) **Clinic Training Visit:** After enrollment, the completion of one month of daily headache diary entries, and reconfirmation by the relevant investigator of the subject's participation in the study, the subject will come to the clinic for an appointment(s) for training on the use of the CVS device. During the clinic visit, the subject will complete a quality of life (QOL) assessment. The assessment will consist of the HIT-6, BAI, BDI-II and Pittsburgh Sleep Quality Assessment questionnaires. The BAI and BDI-II scores will be tallied with the following outcomes:
 - a. Subjects who score 20 or higher on the BDI-II or answer affirmative to questions 9 on the BDI-form will not proceed to randomization and will be withdrawn from the study.
 - b. Subjects who score 16 or higher on the Beck Anxiety Index will not proceed to randomization and will be withdrawn from the study.

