Note: The treatment delivery data (recorded on the SD cards) from the CVS device consists of temperature waveform files that contain actual measured temperature values that were delivered to the earpieces during treatments. This data is an independent record of the expected device performance and is used for confirmation purposes only. The SD card data files also record treatment times and subject compliance, which will be used to calculate the level of treatment compliance. Subjects will *not* be informed that the device monitors treatment compliance.

- **End of Second Treatment Period – Start of Observation Period:** At the end of the second treatment period, all subjects will return their devices to the clinics. The SD cards will be collected. Subjects will be asked to complete the QOL questionnaires again and will be asked to complete a final usability questionnaire.

Subjects will then be asked to continue to make recordings in their headache diaries for an additional 12 weeks.

- **End of Observation Period/End of Study:** Subjects will return to the clinics one final time. They will be asked to complete the QOL questionnaires.

5) Active Treatment Parameters; Placebo Treatments

The following parameters will be set for active treatments using the CVS device:

- A standardized CVS time-varying waveform lasting approximately 19 minutes will be used for all active treatment subjects at all study sites. Treatments will be administered once or twice daily, based upon a subject's randomization assignment. The two daily treatments should ideally be separated by at least one hour.
- The waveform schedule for active treatment subjects will consist of a warm sawtooth delivered to one ear and a cold sawtooth delivered to the other ear. The warm sawtooth will go from body temperature to 42 °C, and the cold sawtooth will go from body temperature to 17 °C. The two waveforms will be delivered simultaneously, but will have different oscillation frequencies. After each two-day period, the warm and cold waveforms will be switched so that the opposite ears will be treated with the different caloric stimulation. Thus every two days the ear receiving the cold stimulus will be switched to the warm stimulus and vice versa.

The following parameters will be set for the placebo treatments using the CVS-M Device:

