An experienced, independent and blinded Statistician will analyze and summarize the daily headache diaries for all subjects and evaluate the primary endpoint and observational aims. A blinded reviewer will analyze and summarize the quality of life data.

The primary aim of this trial is to determine if subjects randomized to the twice-daily active group, have a greater reduction in the number of headache days than those assigned to the twice-daily placebo group. For this study, the reduction in headache days (primary endpoint) is calculated as the number of headache days during the baseline month minus the number of headache days during treatment month three. An intent-to-treat methodology will be employed for the primary aim; however, per protocol analyses will also be conducted for comparison. Analysis of the primary endpoint and the secondary headache-related endpoints assessed in the daily diary will be performed for all subjects that complete at least 25 diary entries or more during the relevant 28-day treatment month. Treatment compliance is defined as completion of at least 50% during

each treatment months (for the per protocol evaluation). Subjects with treatment compliance below 50% during any treatment month will be assigned to the intent-to-treat group only. As accurate assessment of some of the secondary endpoints assessed during study period do not depend on daily headache diary compliance, treatment compliance will be the only criteria for inclusion in the per protocol analysis of those secondary outcomes. Statistical significance will be defined with a Type I error of 5% ($\alpha=0.05$). Wilcoxon rank-sum tests (for non-normal data) or a paired student's t-tests (for normal data) will be used to establish whether the reductions in headache days between the baseline and third treatment month in each treatment arm are statistically significant. Mann-Whitney U tests (for non-normal data) or unpaired student's t-tests (for normal data) will be used to determine whether the reduction in migraine headaches in the twice daily active treatment arm subjects is significantly greater than that observed in the twice daily placebo treatment arm subjects. No interim analyses of efficacy are planned.

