BAI (completed)			

BDI-II scores above 20 or **BAI** scores above 16 after treatment has commenced should be referred to the PI for consultation with [name]. If the subject answers in the affirmative to question 9 of the BDI-II form, he/she should be referred for mental health counseling on that same clinic visit.

SUBJECT ID: _____
DATE: _____SITE #: _____
PROTOCOL NUMBER: _____**Device Treatment at the Clinical Site with new Treatment Card:****Yes No**

Was a new Treatment Card (SD card) inserted into the device before treatment?	Yes	No
Any side effects or AEs reported after device treatment?	Yes	No
Was the device treatment aborted?	Yes	No
Any complaints from subject?	Yes	No
Any concerns about the subject?	Yes	No
If Yes, to any questions above, please provide comment:		

- Review device compliance and proper operation of the device and delivery of treatments.
- Administer Usability Questionnaire after completion of device training.
- Review Daily Headache Diary completion and upload to gmail account each day.
- Collect and return old Treatment card (SD card) from the device to Scion NeuroStim (SNS).

I have reviewed the data from this visit and found the information to be complete and accurate. I verify that all of the tasks have been performed.

Principal Investigator Signature

Date

SUBJECT ID: _____
DATE: _____SITE #: _____
PROTOCOL NUMBER: _____**Phone Contact (Week 18)****A phone call to the subject is required every 2 weeks after Initiation of 2nd Treatment Period**

Date of this phone contact	____	/	____	/	____
----------------------------	------	---	------	---	------

Adverse Events and Concomitant Medication Assessment:	Yes	No
Any Adverse Events (AEs) since last visit?		
If Yes, please complete AE form.		
Any new medications or changes in medications since last visit?		
If Yes, please add medication(s) to the Concomitant Medication form. Acute abortive medications and migraine prophylactic medications should not be changed during the clinical trial.		

Subject Compliance:	Yes	No
Is the subject compliant with daily device treatments?		
Is the subject compliant with Daily Headache Diary and uploads?		
If No, to any questions above, please provide comment:		

- Review device compliance and proper operation of the device and delivery of treatments.
- Review Daily Headache Diary completion and upload to gmail account each day.

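### The Visit 4 form returns each period-1 treatment card to the sponsor at week 16, which opens an unrestricted route to the treatment arm before the period-1 analysis

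*Combined protocol and SAP*

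**What the plan says.** **Where the card goes.** The Visit 4 form (end of week 16) has the site "Collect and return old Treatment card (SD card) from the device to Scion NeuroStim (SNS"). It gives no seal, hold, intermediary or release date. Section 4, item (v), says only that old cards are kept so that compliance can be extracted. It does not say who keeps or reads them, or when.

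**What the card holds.** The note on treatment delivery data in section 4 describes "temperature waveform files that contain actual measured temperature values that were delivered to the earpieces during treatments" and adds: "The SD card data files also record treatment times and subject compliance". It says the delivery record "is used for confirmation purposes only".

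**Who is kept from the assignment.** Section 3 lists the subject, the principal investigator and the statistician. The sponsor is not listed. The Background and Definitions call the trial triple-blinded without naming the three parties.

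**What the sponsor can decide or receive meanwhile.** The Withdrawal Criteria in section 2 include "A subject is significantly non-compliant with the requirements of the protocol (principal investigator & sponsor decision") and "Scion Neurostim discontinues the study or has achieved the targeted enrollment". For the diaries, section 4, item (i), says: "Subjects will be given Scion email accounts to be used for submitting headache diary entries".

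**Analysis timing.** Section 7 places the period-1 analysis at 120 completers. Section 8 says: "No interim analyses of efficacy are planned".

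**The concern.** The primary comparison is twice-daily active against twice-daily placebo, and the period-1 card identifies both arms. The form sends it to the party that issues the accounts through which the outcome diaries are submitted, shares non-compliance withdrawal decisions and can discontinue the study. Cards start to arrive when the first subject reaches week 16, while others are still enrolling or in period 1.

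What is at stake is whether decisions made before the lock can be shown to have been made without knowledge of the arm. Some judgement remains open in that interval. The per-protocol rule in section 8 requires 50% compliance in each treatment month but does not say what the 50% is a percentage of. Section 2 groups subjects with more than 14 headache days separately without saying what this does to the primary analysis. A trial reported as triple-blinded with no interim look should be able to show that its sponsor could not have read the arms.

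**Working it through.** **1. Does one card show the arm?** Section 5 gives active treatment as a warm sawtooth to 42 °C in one ear and a cold sawtooth to 17 °C in the other. Placebo runs the fans and leaves the earpieces unpowered. Measured temperatures therefore separate active from placebo, and treatment times separate once-daily from twice-daily. Together they identify all three arms. The period-2 card collected at Visit 5 does not show who had placebo, because everyone is then on active treatment.

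**2. Is the primary dataset open when the card leaves the site?** Visit 4 falls at 28 + 84 = 112 days, or week 16. That subject's own month 3 is over. For the trial, section 7 sets the analysis at 120 completers, so every card except those of the last completers can arrive earlier.

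**3. Does any text close the route?**

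| Text | What it limits | Restricts sponsor access to the card? |
|---|---|---|
| Section 3, assignment withheld from three parties | Subject, investigator, statistician | No; sponsor not listed |
| Section 4 note, confirmation only | Use of the delivery record | No |
| Section 4 (v), old cards kept | Nothing on holder, reader or date | No |
| Section 8, blinded independent statistician | Who runs the primary analysis | No |
| Section 8, no interim efficacy analysis | Planned looks | No |

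**4. The plan's own power figure.** Section 8 gives 40 per arm, SD 3.36, difference 2.13 days, alpha 0.05 and 80% power. The standard error is 3.36 × √(2/40) = 0.751, and 2.13 / 0.751 = 2.835. Normal power is Φ(2.835 − 1.960) = 80.9%; the two-sample t-test gives 79.95%. The figure reproduces as two-sided (one-sided would give 88.3%), and this point does not change it.

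**5. What could the route do to type I error?** This is a hypothetical. Simulate no effect with normal data, SD 3.36, at most 40 per arm, a two-sided t-test at 5% and 60,000 runs. At each look, if p < 0.05 in those who have finished month 3, enrolment closes. Subjects already randomized then reach month 3 and enter the final intent-to-treat test. If no look crosses, the test is at 40 per arm. The documents give no accrual rate, so the number pending per arm is an assumption, shown as a range.

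| Looks (per arm) | 0 pending | 5 pending | 10 pending |
|---|---|---|---|
| 40 only (as planned) | 5.1% | – | – |
| 30, 35, 40 | 8.2% | 5.7% | 5.1% |
| 20, 25, 30, 35, 40 | 11.4% | 6.8% | 5.9% |
| Every 2 from 20 to 40 | 13.0% | 7.0% | 5.9% |

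The simulation standard error is √(0.05 × 0.95 / 60,000) = 0.09 points near 5% and √(0.13 × 0.87 / 60,000) = 0.14 points near 13%. In the second row, 10 pending gives the planned error because a stop at 30 still ends with 30 + 10 = 40 per arm. Zero pending is a limiting case: the outcome is read over the last 28 of 84 treatment days, so subjects will normally be in the pipeline at any look.

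**The case against.** The case on the other side is substantial.

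- **No rule is broken.** A reader might infer that the sponsor's blind is breached, or that the sponsor watches the running difference. The documents support neither. They never say that the sponsor is blinded. They do not say who receives or tabulates the diary images sent through the sponsor-issued accounts. They assign the diary analysis to an independent, blinded statistician. This stands.
- **The card comes too late to affect that subject's period 1.** A reader might infer that the sponsor could use it to decide that subject's period-1 withdrawal. It could not: the form collects the card at Visit 4, and period-1 compliance is reviewed by phone. A withdrawal after Visit 4 does not by itself remove month-3 data already recorded from the intent-to-treat analysis. This also stands.
- **The analysis point is set.** Section 7 names 120 completers and section 8 plans no interim efficacy analysis, so stopping on a favourable look would depart from the plan. This stands, although section 3 gives the size as up to 120 and section 2 lets the sponsor discontinue the study.
- **The per-protocol rule is preset and secondary.** This stands in part. The 50% threshold is fixed, but its denominator is not stated.
- **The card is needed for compliance.** This is true, and the fix has to allow for it.

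These points limit the likely harm. None of them restricts who may read a period-1 card, or when.

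**Conclusion.** The point holds as an access gap. The form sends arm-revealing data to the sponsor before the period-1 analysis, and no text withholds it. The Visit 4 form and section 4 (v) also need to agree on who holds the card.

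The size is modest. A reader might infer that the route raises the 5% type I error to 8%, 11% or 13%. Those values need two things: that the sponsor closes enrolment at the first significant look, which the documents do not suggest, and that no randomized subject is then awaiting month 3, which the 84-day treatment period makes unlikely. With an assumed 5 to 10 per arm pending, the same looks give about 5% to 7%. The 8% to 13% range is at most a worst case and should not be cited as the expected effect.

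What remains is credibility: the sponsor could not show from the plan that later withdrawals, the per-protocol list and any decision to end enrolment or the study were made without knowledge of the arm. This should be fixed because it is cheap. It does not invalidate the design or the primary test.

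**What to change.** 1. **Visit 4 form.** Replace the return to the sponsor with: seal the old card under subject ID; the unblinded site coordinator holds it until the period-1 diary data, withdrawals and per-protocol list are locked. The Early Termination form asks for study materials back without saying where the card goes; apply the same hold to anyone who leaves in period 1.
2. **Section 4 (v).** Name the same holder and release point.
3. **Early compliance, if needed.** Release only the percentage of assigned sessions completed in each treatment month. Do not release waveforms or session times, because times show once-daily versus twice-daily use. The unblinded coordinator, or another unblinded person without diary access or a decision role, should produce the percentage.
4. **Section 8.** Add one sentence: no sponsor staff with diary access, or with a role in withdrawal or enrolment decisions, read period-1 card files before that lock.

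The cost is a changed line on the form, an aligned sentence in section 4 and a new one in section 8. Visits, sample size and the primary test are unchanged. The downside is that the sponsor's confirmation of device output from period-1 cards waits until the lock. The documents do not say what is needed to extract a compliance percentage at the site, so that must be checked first.
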